A Sequential Two-Stage Dose Escalation Study to Evaluate the Safety and Efficacy of Ruxolitinib for the Treatment of Chronic Myelomonocytic Leukemia (CMML) and Cataloging the Molecular Consequences of JAK2 Inhibition in Chronic Myelomonocytic Leukemia: A Correlative Study Identifying Targetable CMML Sub-Clones by Leveraging GM-CSF Dependent pSTAT Hypersensitivity

NCT01776723

Version 15

October 28, 2016

TITLE: A Sequential Two-Stage Dose Escalation Study to Evaluate the Safety and Efficacy of Ruxolitinib for the treatment of Chronic Myelomonocytic Leukemia (CMML) and Cataloging the Molecular Consequences of JAK2 Inhibition in Chronic Myelomonocytic Leukemia: A Correlative Study Identifying Targetable CMML Sub-Clones by Leveraging GM-CSF Dependent pSTAT Hypersensitivity

Sponsor: H. Lee Moffitt Cancer Center & Research Institute

Funding: INCYTE

*Principal Investigator: [name]

H. Lee Moffitt Cancer Center & Research Institute

[name]

[contact]

e-mail address: [contact]

Co-Investigators: [name]

[name] [name] [name] [name]

[name], BS

[name]

Statistician: [name]

Version: 15

Date: 10/28/2016

Table of Contents

1	OBJECTIVES	•••••		•••••	•••••	•••••	7
2	BACKGROUND				8		
3	STUDY ENDPOINT	S			14		
4	PATIENT SELECTIO	N					15
5	STUDY DESIGN			•••••	17		
6	TREATMENT PLAN	I					17
7	DURATION OF THI	ERAPY					22
8	DURATION OF FOI	LLOW-UP .					23
9	CRITERIA FOR REN						
10	DOSING DELAYS/	MODIFICA	TIONS				24
11	ADVERSE EVENTS:	REPORTI	NG REQUIREM	ENTS			27
12	PHARMACEUTICA	L INFORM	ATION				32
13	STUDY CALENDAR						32
14	MEASUREMENT O	F EFFECT					37
15	STATISTICAL CONS	SIDERATIO	NS				38
16	LABORATORY COF	RRELATES .					39
17	REGULATORY CON	ISIDERATION	ONS				43
18	REFERENCES						46
19	APPENDIX A						49
20	APPENDIX B	• • • • • • • • • • • • • • • • • • • •					50
21	APPENDIX C: CYP3	BA4 STRON	IG INHIBITORS				52
22	APPENDIX D: SYM						
 23	APPENDIX E: WHO						

Protocol Synopsis

Title: A Sequential Two-Stage Dose Escalation Study to Evaluate the Safety and Efficacy of Ruxolitinib for the treatment of Chronic Myelomonocytic Leukemia (CMML)

(CIVIIVIE)	n' ol' d												
Study	Primary Objectives: 1. To determine the sofety and telembility of myselitinih in CMMI subjects at discussion.												
Objectives	1. To determine the safety and tolerability of ruxolitinib in CMML subjects at diagnosis or												
	relapse. (phase I)												
	2. To determine overall best response rates as measured by the international working group												
	criteria (2006). (phase II)												
	Secondary Objectives:												
	1. To determine the time to AML transformation of subjects on Ruxolitinib.												
	2. To determine the median overall survival.												
	3. To determine the duration of response.												
	4. To determine the change in symptom score from baseline to best response.												
	5. To determine the change in spleen length at 16 weeks												
	6. To determine the change in downstream targets of JAK2 on ruxolitinib.												
	7. To determine if the in vitro activity of ruxolitinib correlates to response rates.												
	8. To determine if a correlation exist between the presence of the known recurrent												
	mutations (JAK2, c-CBL, N-RAS, K-RAS, RUNX-1, TET2, SRSF2, EZH2, ASXL1,												
	and DNMT3a) and response to ruxolitinib												
	9. To determine non-V617F JAK2 mutations at end of study or progression and their												
	clinical relevance in the context of ruxolitinib.												
	chinear relevance in the context of fuxontinio.												
Study	Primary												
Endpoints	1. The maximum tolerated dose (MTD) of ruxolitinib for the treatment of CMML.												
Ziiupoiiio	The MTD is defined as the highest dose where less than 33% of subjects												
	experience a drug related predefined dose limited toxicity (DLT).												
	2. Proportion of subject achieving a hematological response, partial response,												
	complete response, or stable disease by the IWG 2006 criteria (see appendix B)												
	Secondary												
	3. Acute myeloid leukemia (AML) transformation according to WHO criteria.												
	4. Overall survival (OS).												
	5. Duration of response.												
	6. The Myeloproliferative Neoplasms Symptom Assessment Form (MPN-SAF) at												
	baseline and at best response.												
	7. >50% decrease in splenic length as measured by physical exam if applicable												
	8. The suppression of pSTAT5 intracellular signaling after ruxolitinib in CMML												
	subjects (pretreatment, at 1-2hr post treatment, cycle 2, cycle 4, and												
	progression.)												
1	9. Determine number of colonies formed in the presence of GM-CSF and/or												
	ruxolitinib (pretreatment and progression) as a future predictor of response.												
	10. Mutational status in our CMML subjects by sanger sequencing of JAK2, c-												
1	CBL, N-RAS, K-RAS,RUNX-1, TET2, SRSF2, EZH2, ASXL1, and DNMT3a												
	(pretreatment and progression).												
	11. Mutational status of JAK2 tyrosine kinase at time of progression by deep												
	sequencing of JAK2 to include M929I, Y931C, G935R, R938L, I960V, E985K.												
	(pretreatment and at progression)												
F11. 01.000													
Eligibility	Inclusion Criteria:												
Criteria	1. Confirmed diagnosis of CMML using the World Health Organization (WHO)												

- classification (appendix E).
- 2. Age >18 years at the time of obtaining informed consent.
- 3. Must be able to adhere to the study visit schedule and other protocol requirements.
- 4. Subjects must be able to provide adequate BM aspirate and biopsy specimens for histopathological analysis and standard cytogenetic analysis during the screening procedure.
- 5. An Eastern Cooperative Oncology Group (ECOG) performance status score of 0, 1, or 2 is required.
- 6. Women of childbearing potential must agree to use two reliable forms of contraception simultaneously or to practice complete abstinence from heterosexual intercourse 1) for at least 28 days before starting study drug; 2) while participating in the study; and 3) for at least 28 days after discontinuation from the study. The two methods of reliable contraception must include one highly effective method (i.e. intrauterine device [IUD], hormonal [birth control pills, injections, or implants], tubal ligation, partner's vasectomy) and one additional effective (barrier) method (i.e. latex condom, diaphragm, cervical cap).
- 7. Must understand and voluntarily sign an informed consent form.
- 8. Must have a life expectancy of greater than 3 months at time of screening.

Exclusion Criteria:

- 1. Any of the following lab abnormalities:
 - Platelet count of less than 35,000/uL
 - Absolute Neutrophil Count (ANC) less than 250/uL
 - Serum Creatinine > 2.0
 - Serum total bilirubin >1.5x ULN
- 2. Use of cytotoxic chemotherapeutic agents, or experimental agents (agents that are not commercially available) for the treatment of CMML within 28 days of the first day of study drug treatment.
- 3. Prior history of metastatic malignancy in past 2 years
- 4. Any serious medical condition or psychiatric illness that will prevent the subject from signing the informed consent form or will place the subject at unacceptable risk if he/she participates in the study.
- 5. Concurrent use of GM-CSF. G-CSF could be used for the short-term management of neutropenic infection. Stable doses of erythropoietin stimulating agents that were started >8 weeks from first ruxolitinib dose or corticosteroids that were being administered prior to screening are allowed.
- 6. Uncontrolled current illness including, but not limited to ongoing or active infection, symptomatic congestive heart failure, unstable angina pectoris, cardiac arrhythmia, or psychiatric illness/social situations that would limit compliance with study requirements.
- 7. Pregnant women are excluded from this study because ruxolitinib has not been studied in pregnant subjects. Because there is an unknown but potential risk for adverse events in nursing infants secondary to treatment of the mother with ruxolitinib, breastfeeding should be discontinued if the mother is treated with ruxolitinib.
- 8. Patients who have participated in other interventional (treatment-related) clinical trials within 30 days of enrollment are excluded.

Baseline Assessment (within 4 weeks of starting treatment)

- 1. Medical history including:
- a. disease characteristics such as first diagnosis of CMML, WHO/FAB subtype, IPSS score, MD Anderson Scoring System (MDASC), prior treatments.
- b. ECOG performance status.
- c. The Myeloproliferative Neoplasms Symptom Assessment Form (MPN-SAF) at baseline and at best response.
- d. Concurrent medication review.
- 2. Routine physical examination to include vital signs, height and weight.
- 3. Bone marrow examination, including cytomorphology, cytogenetic assessment,

and flow cytometry analysis. 4. Laboratory assessments: • Hematology to include platelet count, hemoglobin, hematocrit, white blood cells (WBC) and WBC differential (including: neutrophils, eosinophils, basophils, lymphocytes and monocytes), INR, PT, PTT, and reticulocyte count. • Clinical chemistries including BUN/urea, creatinine, sodium, potassium, alkaline phosphatase, alanine aminotransferase (ALT), aspartate aminotransferase (AST), total bilirubin, total bilirubin, albumin. • Urine or serum pregnancy test for females of childbearing potential will be performed at Screening or on Day 1, prior to first dose of study medication. 5. Review and record any blood and blood supportive care products for the prior 8 weeks. Treatment will be administered on an outpatient basis. Reported adverse events and potential Treatment risks are described in Section 11. Appropriate dose modifications for ruxolitinib are described in nlan Section 10. No investigational or commercial agents or therapies other than those described below may be administered with the intent to treat the patient's CMML. Ruxolitinib will be supplied by INCYTE as 5mg tablets containing ruxolitinib. Ruxolitinib will be self-administered as a twice-daily oral dose for a continuous treatment cycle. Ruxolitinib tablets will be taken approximately 12 hours apart (morning and night). Subjects will not take the morning dose of ruxolitinib at the first regularly scheduled visit. Drug will be administered in the clinic in order to obtain adequate biomarker assessment. On all other days corresponding to study visits, subjects will take the morning dose of study drug prior to the visit, and will note on the subject reminder card the time that medications were taken. Subjects will also be instructed to take ruxolitinib without respect to food, as previous data demonstrate no change in drug kinetics or absorption. The first patient will be given 10 mg/day divided in equal BID doses. Dose escalation guidelines are detailed below in section 10. In phase II of the study, a maximum of 29 subjects will be treated at the MTD identified in phase I. See study calendar for assessment on study. All subjects enrolled in phase 1 will start treatment on the assigned dose per cohort based on the Dose delay/modif dose escalation algorithm provided. Dose delays/modifications will not be allowed in phase 1 as it -ications will interfere with the primary endpoint of this study. Dose delays/modifications are allowed for those subjects enrolled in phase II as described in section 6. Definition Dose-limiting toxicity (DLT) is defined as any grade 4 hematologic toxicity and any grade 3 or of Dosegreater non-hematologic toxicity except nausea that is controlled by antiemetic therapy based on Limiting the NCI Common Terminology Criteria for Adverse Events (CTCAE) version 4.0. Grade 3 metabolic/electrolyte abnormalities that are not clinically significant, and are adequately Toxicity controlled within 72 hours are not to be considered a DLT. To discern disease specific versus drug specific myelosuppression, Grade 4 thrombocytopenia will be defined as a decrease of > 50% of baseline and a level of < 25,000/uL. Grade 4 neutropenia will be defined as a decrease of $\ge 50\%$ of baseline and a level of <500/uL. Subjects will be evaluated for DLTs during the first and second cycles of therapy, i.e. 8 weeks for purpose of deciding the dose for next cohort (see dose escalation schema) but DLTs will continue to be evaluated and reported through all cycles on **Duration of** Subjects will be treated for a total of 16 weeks. For subjects responding at week 16, treatment may continue until one of the following criteria applies: **Therapy** Dose-limiting toxicity is reached, Inter-current illness that prevents further administration of treatment, Unacceptable adverse event(s), Patient decides to withdraw from the study, or General or specific changes in the patient's condition render the patient unacceptable for further treatment in the judgment of the investigator. Evidence of disease progression by the IWG 2006 criteria. Subjects who wish not to continue treatment will complete their end of study visit at week 16.

Subjects who were not enrolled in the MTD cohort can increase to the MTD after week 16 if the participant still meets the eligibility criteria. Responding patients will be able to continue treatment until marketing approval of ruxolitinib for CMML. **Duration of** Subjects will be followed as per calendar on treatment for 17 weeks. After 17 weeks, subjects who continue on study will be followed monthly. Off study data on AML transformation and Follow-Up overall survival will be updated every 6 months or until death, whichever occurs first. Subjects removed from the study for unacceptable adverse events will be followed until resolution or stabilization of the adverse event. Criteria for Removal from Study Study drug treatment can continue for subjects receiving clinical benefit, unless; one or more withdrawal criteria are met, or at the subject's discretion, or if the study is terminated, or until the marketing approval for CMML *Subject Completion A subject will be considered to have completed the study if the subject meets at least 1 of the following criteria: - The subject has completed 16 weeks of treatment with study medication with no improvement. - The subject died during the study. - The subject withdrew from study including subjects who experience a DLT. - The subject experienced an AE that lead to withdrawal from the study. *Subject Withdrawal from Study A subject may voluntarily withdraw from study medication or withdraw consent from the study at any time. The investigator may also, at his or her discretion, discontinue a subject from participating in the study at any time. The investigator will record the date and the reason for subject withdrawal from the study. *Subject Withdrawal from Study Medication If the subject is permanently withdrawn from treatment with study medication, but does not withdraw consent, the investigator must make every effort to have the subject complete all withdrawal assessments at the time of withdrawal, and complete all scheduled follow-up visits. Treatment with study medication must be discontinued if (Withdrawal Criteria): • No clinical benefit has been attained after 16 weeks of treatment. • Evidence of Disease progression according to IWG 2006 criteria. a subject experiences a DLT. • a subject becomes pregnant. • a subject is significantly non-compliant with the requirements of the protocol; • a subject has an adverse experience that would, in the investigator's judgment, make continued participation in the study an unacceptable risk See calendar page 36 Follow up on study **Statistics Study Design:** This study will use a dose escalation, "rolling 6" design in Phase 1. Subjects will be allocated to starting doses of 10 mg/d to 40mg/d (divided in two equal doses) escalated by 10 mg/day for each cohort according to the predetermined algorithm outlined below in Table 1 (section 6.4). Each cohort will include 6 subjects. After testing the treatment dose on 10 patients in the first stage, the trial will be terminated if 1 or fewer desired respond. If the trial goes on to the second stage, a total of 29 patients will be studied. If the total number responding is less than or equal to 5, the drug is rejected. *Sample Size/Accrual Rate

If dose escalation is completed as planned a maximum of 53 (24 phase 1 and 29 in phase 2) are expected to enroll at a rate of 3 subjects every 1 month for stage I. The first phase of the stage II will recruit 10 subjects at the MTD. If 1 response are seen by 17 weeks on Ruxolitinib, then a total of 29 subjects will be accrued at the MTD to determine efficacy. Maximum accrual is 53 subjects.

Analysis of the following secondary endpoints will be of exploratory nature:

- 1. Acute myeloid leukemia (AML) transformation according to WHO criteria.
- 2. Overall survival (OS).
- 3. Duration of response.
- 4. The Myeloproliferative Neoplasms Symptom Assessment Form (MPN-SAF) at baseline and at best response.
- 5. >50% decrease in splenic length as measured by physical exam
- 6. The suppression of pSTAT5 intracellular signaling after ruxolitinib in CMML subjects (pretreatment, at 1-2hr post treatment, cycle 2, cycle 4, and progression.)
- 7. Determine number of colonies formed in the presence of GM-CSF and/or ruxolitinib (pretreatment and progression) as a future predictor of response.
- 8. Mutational status in our CMML subjects by sanger sequencing of JAK2V617F, c-CBL, N-RAS, K-RAS,RUNX-1, TET2, SRSF2, EZH2, ASXL1, and DNMT3a (pretreatment and progression).
- 9. Mutational status of JAK2 tyrosine kinase at time of progression by deep sequencing of JAK2 to include M929I, Y931C, G935R, R938L, I960V, E985K. (pretreatment and at progression)

Laboratory Correlates

Phases 1 and 2

The pharmacokinetics of ruxolitinib has been extensively studied in subjects with myeloid malignancies. Ruxolitinib is quickly absorbed with peak levels at 1 to 3 hours after ingestion of the tablet. Because of this, subjects will take their first dose of ruxolitinib in the clinic. At that time, and three hours after taking the tablet, peripheral blood will be collected and processed in the lab of [name] in the Stabile Research Building (SRB) at the Moffitt Cancer and Research Institute as described in section 16.

Using processed peripheral blood, pSTAT5 will be measured by flow cytometry at the time of tablet ingestion and 3 hours later. Bone marrow aspirates will also be used to perform colony formation assay as described in section 16 and to collect a minimum of 100 ug of DNA to interrogate the mutational status of the cohort studied as described in section 16.

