5 STUDY DESIGN

This is a phase 1/2, two-stage, sequential cohort dose escalation study. In phase 1, subjects will be allocated to BID doses of 10 mg/d up to 40mg/d. The starting dose will be 10 mg/d (5mg BID). Each cohort will include up to 6 subjects. Once MTD is reached, 10 additional subjects will be treated during the first stage of phase 2 (stage 1) at the MTD. The tiral will be terminated if 1 or fewer respond. If the trial goes on to the second stage, a total of 29 patients will be studied to determine efficacy in phase 2.

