15.2 Sample Size/Accrual Rate

If dose escalation is completed as planned, no more than 53 subjects are expected to enroll onto this study at a rate of approximately 3 subjects every month. For the Phase 2 study the Simon's optimal two-stage design will be employed to test the null hypothesis that response rate (RR) equals to 10% versus the alternative that RR equals to 30%. If the treatment is actually not effective, there is a 0.05 probability of concluding that it is. If the drug is actually effective, there is a 0.19 probability of concluding that it is not. The probability of early terminating the trial at the end of first stage under the null is 0.74. After testing the treatment dose on 10 patients in the first stage, the trial will be terminated if 1 or fewer desired respond. If the trial goes on to the second stage, a total of 29 patients will be studied. If the total number responding is less than or equal to 5, the drug is rejected. A sample size of 29 from Phase 2 produces a two-sided 95% CI with a width equal to 0.38 (±19) when the sample proportion is 0.50 that is the maximum width for a CI with an given sample sizes.

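### The synopsis accrual paragraph opens stage 2 at 1 response in 10, a count at which the rest of the plan stops phase 2

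*Combined protocol and SAP*

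**What the plan says.** Phase 2 is a Simon optimal two-stage design. Section 15.2 uses it to "test the null hypothesis that response rate (RR) equals to 10% versus the alternative that RR equals to 30"%. It gives the interim rule as "After testing the treatment dose on 10 patients in the first stage, the trial will be terminated if 1 or fewer desired respond", a total of 29 if the trial continues, and the final rule as "If the total number responding is less than or equal to 5, the drug is rejected". It states a type I error of 0.05 and two further figures: "If the drug is actually effective, there is a 0.19 probability of concluding that it is not" and "The probability of early terminating the trial at the end of first stage under the null is 0.74".

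The interim rule appears in three other places:

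- Synopsis, Statistics, Study Design paragraph: "the trial will be terminated if 1 or fewer desired respond".
- Section 5: "The tiral will be terminated if 1 or fewer respond".
- Synopsis, Sample Size/Accrual Rate paragraph, directly after the Study Design paragraph: "If 1 response are seen by 17 weeks on Ruxolitinib, then a total of 29 subjects will be accrued at the MTD".

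The first two agree with section 15.2. The third does not. No order of precedence among these texts is stated.

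**The concern.** At exactly 1 response in 10, the accrual paragraph continues to 29 while the other three texts stop. This is the only futility gate in phase 2, and the count in dispute is an ordinary one: at the null rate it is the single most likely stage 1 result, narrowly ahead of no responses. The accrual paragraph is also the statement of the gate that carries a time point (17 weeks), so staff timing the interim decision have a reason to consult it. Anyone who applied it would run a design with operating characteristics that section 15.2 does not describe.

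**Working it through.** **Inputs.** All come from section 15.2: p0 = 0.10, p1 = 0.30, n1 = 10, n = 29 (so 19 subjects in stage 2), and the drug is rejected at 5 or fewer responses in total. The two candidate interim rules are:

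- Rule A: stop at 1 or fewer (synopsis Study Design, section 5, section 15.2).
- Rule B: stop only at 0, that is, continue at 1 or more. This is the accrual paragraph read as a minimum, paired with the unchanged final cut-off.

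**Formulas.** X1 ~ Bin(10, p), X2 ~ Bin(19, p), and r1 is the largest stage 1 count at which the trial stops.

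- Early termination: PET = P(X1 ≤ r1).
- Probability of declaring activity: sum over x > r1 of P(X1 = x) × P(X2 ≥ 6 − x).
- Expected sample size: 10 + 19 × (1 − PET).

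**Step 1: reproduce section 15.2 under rule A.**

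PET at p = 0.10 is P(X1 = 0) + P(X1 = 1) = 0.3487 + 0.3874 = 0.7361.

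| Stage 1 responses x | P(X1 = x), p = 0.10 | P(X2 ≥ 6 − x), p = 0.10 | Product, p = 0.10 | Product, p = 0.30 |
|---|---|---|---|---|
| 2 | 0.1937 | 0.1150 | 0.0223 | 0.2024 |
| 3 | 0.0574 | 0.2946 | 0.0169 | 0.2545 |
| 4 | 0.0112 | 0.5797 | 0.0065 | 0.1980 |
| 5 | 0.0015 | 0.8649 | 0.0013 | 0.1028 |
| 6 or more | 0.0001 | 1 | 0.0001 | 0.0473 |
| Sum | | | 0.0471 | 0.8051 (from unrounded terms) |

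So alpha = 0.0471 and beta = 1 − 0.8051 = 0.1949. The stated 0.74, 0.05 and 0.19 are reproduced. A search over total sizes of 15 to 35, with alpha at most 0.05 and power at least 0.80, also returns 1/10 then 5/29 as the design with the smallest expected sample size under the null.

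**Step 2: add the disputed path.** Rule B differs from rule A only by the path through exactly 1 of 10, which then needs at least 5 of 19.

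- At 10%: 0.3874 × 0.0352 = 0.0136, so alpha = 0.0471 + 0.0136 = 0.0607.
- At 30%: 0.1211 × 0.7178 = 0.0869, so power = 0.8051 + 0.0869 = 0.8920.

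**Step 3: compare.**

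| | Section 15.2 states | Rule A | Rule B |
|---|---|---|---|
| PET under the null | 0.74 | 0.7361 | 0.3487 |
| Alpha | 0.05 | 0.0471 | 0.0607 |
| Beta | 0.19 | 0.1949 | 0.1080 |
| Expected N at 10% | not stated | 10 + 19 × 0.2639 = 15.0 | 10 + 19 × 0.6513 = 22.4 |
| Expected N at 30% | not stated | 26.2 | 28.5 |

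Rule B reproduces none of the three stated figures. The literal reading, continuing only at exactly 1, does no better: alpha would be 0.014 and power 0.087.

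**The case against.** The strongest objection is that the conflict rests on one ungrammatical sentence in a synopsis table that was visibly damaged when the PDF was read. Comparison symbols vary elsewhere in the text: the creatinine exclusion is a strict inequality in the synopsis but not in section 4.2.1.3, and section 14 prints an impossible blast threshold of less than 0%. If a greater-than sign has dropped out before the 1, the sentence agrees with the other three. This possibility cannot be excluded from the text alone, so the finding is confined to the text as printed. A lost greater-than-or-equal sign would leave the conflict in place, and the plural verb fits either symbol.

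It can also be said that the rule is given correctly three times, once just before the disputed sentence, and that no calculation in the plan is wrong. Both points are true. They show that the intended rule can be recovered and that this is a wording error in a decision rule, not a fault in the sample-size calculation. They do not remove a contradictory go/no-go instruction from current text.

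Finally, the accrual paragraph does not say at least 1 and does not repeat the final cut-off, so the figures for rule B depend on a reading. That is correct. The conflict at exactly 1 of 10 does not depend on it.

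**Conclusion.** The concern holds for the text as printed. The accrual paragraph and the other three statements give opposite decisions at exactly 1 response in 10, which has probability 0.387 at a 10% response rate and 0.121 at 30%. Section 15.2 is internally correct, and its figures identify stopping at 1 or fewer as the intended rule.

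On the assumption that the accrual paragraph means 1 or more, with the same final cut-off, following it would cost 0.0136 in alpha (taking it above the stated 0.05) and about 7.4 subjects in expected size under the null (22.4 − 15.0), and would gain 0.0869 in power. At a 10% response rate, a trial that continued from 1 of 10 would have only a 0.035 chance of reaching 6 of 29; at 30% that chance is 0.718. Because the conflict sits on the only phase 2 futility gate, at its most likely null result, it should be corrected.

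**What to change.** First check the source file for a comparator lost before the 1. If it reads as more than 1, the rules already agree and only clearer wording is needed. Otherwise correct the threshold in the synopsis Sample Size/Accrual Rate paragraph and keep its time point, for example: *If 2 or more of the first 10 phase 2 subjects have responded by 17 weeks on ruxolitinib, accrual continues to a total of 29 at the MTD; with 1 or fewer responses the trial stops.*

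The threshold in the synopsis Study Design paragraph, section 5 and section 15.2 stays as it is. The cost is one corrected sentence, with no change to the design, the sample size or the stated error rates.
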